Used in the above way, it has been shown that the VAS is a proper ratio scale. Like a thermometer, this means that its two ends are rooted, and a doubling of the score does accurately reflect a doubling of the pain. Consequently, sensitive t-tests and ANOVA methods can be used in the analysis, so that significant differences can be identified with relatively small sample sizes or small differences between groups.

Source: *Measuring Pain* by Adrian White, *Acupuncture in Medicine*, November 1998 – Vol 16 No. 2

The subject is instructed to refrain from consuming any pain relief medication within 4 hours of recording a required VAS Degree of Pain Rating to ensure that the effect of the pain relief medication does not influence any potential treatment effect of the study procedure with the Erchonia® FX-635™ as evidenced through the VAS ratings. The subject may take a dosage of his or her study rescue pain relief medication immediately after recording a VAS rating, if needed.

The study Principal Investigator will have the sole responsibility of measuring and recording the subject's VAS markings according to the guidance document titled: "Instructions for Principal Investigators for Measuring and Recording Visual Analog Scale (Vas) Ratings in an Erchonia Corporation Sponsored Clinical Study" as contained in Appendix B of this protocol.

NEUROPATHIC PAIN SYMPTOM INVENTORY (NPSI): The NPSI was developed in 2004 by Bouhassira Didier to evaluate the different symptoms of neuropathic pain in adults. It is a 12-item self-administered patient-reported outcome (PRO) assessment tool with a recall/ observation period of over the past 24 hours. It contains 10 descriptors representing 5 distinct dimensions on the basis of factor analysis: burning pain, deep pain, paroxysmal pain, evoked pain, paresthesia/dysesthesia, and 2 temporal items designed to assess pain duration and the number of pain paroxysms. The NPSI has been validated in patients with definite neuropathic pain of peripheral or central origin.

The development and validation of the NPSI is contained in the abstract below:

Development and validation of the Neuropathic Pain Symptom Inventory.

Bouhassira D, Attal N, Fermanian J, Alchaar H, Gautron M, Masquelier E, Rostaing S, Lanteri-Minet M, Collin E, Grisart J, Boureau F.
Pain. 2004 Apr;108(3):248-57.

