This study describes the development and validation of the Neuropathic Pain Symptom Inventory (NPSI), a new self-questionnaire specifically designed to evaluate the different symptoms of neuropathic pain. Following a development phase and a pilot study, we generated a list of descriptors reflecting spontaneous ongoing or paroxysmal pain, evoked pain (i.e. mechanical and thermal allodynia/hyperalgesia) and dysesthesia/paresthesia. Each of these items was quantified on a (0-10) numerical scale. The validation procedure was performed in 176 consecutive patients with neuropathic pain of peripheral (n = 120) or central (n = 56) origin, recruited in five pain centers in France and Belgium. It included: (i) assessment of the test-retest reliability of each item, (ii) determination of the factorial structure of the questionnaire and analysis of convergent and divergent validities (i.e. construct validity), and (iii) evaluation of the

ability of the NPSI to detect the effects of treatment (i.e. sensitivity to change). The final version of the NPSI includes 10 descriptors (plus two temporal items) that allow discrimination and quantification of five distinct clinically relevant dimensions of neuropathic pain syndromes and that are sensitive to treatment. The psychometric properties of the NPSI suggest that it might be used to characterize subgroups of neuropathic pain patients and verify whether they respond differentially to various pharmacological agents or other therapeutic interventions.

PMID: 15030944

The full article and the NPSI Assessment tool are contained in **Appendix C** of this clinical study protocol.

SUBJECT DAILY DIARY: Commencing upon administration of the first Erchonia® FX-635™ laser procedure through to completion of the 4-week post-procedure evaluation phase, for a total of 10 consecutive weeks, the subject will be required to complete a Subject Daily Diary at home, recording the following information, as applicable:

- ✓ *Rescue Pain Medication Use:* The subject will record each time a dose of the study rescue pain medication is taken as needed to manage foot pain.
- ✓ *Confirmation of Abstinence from Other Pain Medication Use:* The subject will confirm at the end of each day that he or she refrained from consuming any OTC and/or prescription medication(s) for the indication of pain relief other than the study pain relief rescue medication during that day

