Subjects will be instructed not to take a dose of any other over-the-counter or prescription medications for the indication of pain relief, including NSAIDs, over the course of study participation.

Subjects will be instructed not to record a VAS pain rating (whenever indicated) any sooner than six hours after they have consumed a dosage of the study pain relief rescue medication. This is to ensure that the effect of the pain relief medication does not influence the effect of the study procedures with the Erchonia® FX-635™ Laser device. That is, a VAS rating is only to be recorded once the effect of any previously-consumed rescue pain medication has dissipated. The subject will be able to take another dosage of the study pain relief rescue medication immediately after recording the VAS rating, if needed.

Throughout the course of his or her study participation, a subject can continue to take any other over-the-counter and/or prescription medication(s) that he or she usually takes for any other (non-pain relief) indication(s), as he or she usually takes them, as reported at Baseline evaluation and approved by the study investigator. Subjects will be required to record any deviations from Baseline reported medication use throughout the course of study participation.

STUDY PROCEDURE PROTOCOL

PRE-PROCEDURE ACTIVITIES

The pre-procedure activities will be conducted at the test site prior to administration of the initial study procedure with the Erchonia® FX-635™.

STUDY QUALIFICATION

SIGNING OF INFORMED CONSENT FORM

The PI will commence by presenting and reviewing in detail the items in the informed consent form with the individual and answer any questions he or she may have. To proceed, the individual must willingly sign the informed consent form.

It is important the subject is aware of the level of commitment they will need in order to partake in this study. This information is detailed in the Informed Consent Form, but the PI should also stress to the subject the number, frequency and length of the visits to minimize future Protocol Deviations due to scheduling conflicts. The PI should also stress the importance of completing the At Home Measures and maintaining the Daily Diaries as completely as possible to reduce questions regarding authenticity.

ASSIGNMENT OF SUBJECT IDENTIFICATION NUMBER

The subject will be assigned a unique subject identification number based upon his or her order of entry into the study.

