8. Subject has been on a stable dosage of any of the following prescription medications or any equivalent agents for at least 90 days prior to initiation of the study procedure administration with the Erchonia FX-635™ and is willing and able to maintain that stable dosage throughout study participation OR subject has not used or is willing to abstain from using any of the following prescription medications or any equivalent agents for 30 days prior to initiation of the study procedure administration with the Erchonia FX-635™:
 - ✓ Neurontin
 - ✓ Lyrica
 - ✓ Tramadol
 - ✓ Opioid medicines such as Ultram and Ultracet
9. Subject has not received or is willing to abstain from receiving any injections of local anesthetics such as lidocaine within 30 days prior to initiation of the study procedure administration with the Erchonia FX-635™.
10. Subject is able and willing to take over-the-counter Regular Strength Tylenol® tablets to manage his or her pain, as needed, throughout the course of study participation.
11. Subject is willing and able to refrain from consuming any over-the-counter and/or prescription medications including muscle relaxants and/or herbal supplements and/or recreational and medical drugs including cannabis intended for the relief of pain and/or inflammation throughout the course of study participation, except for the study-specific pain relief medication of over-the-counter Tylenol.
12. Subject is willing and able to refrain from engaging in any non-study procedure therapies for the management of his or her foot pain throughout the course of study participation, including conventional therapies such as physical therapy, occupational therapy and hot or cold packs, as well as alternative therapies such as chiropractic care and acupuncture.
13. Subject agrees to refrain from taking a dosage of the study rescue pain medication of over-the-counter Regular Strength Tylenol® tablets for at least 6 hours before a scheduled VAS foot pain rating is to be recorded. The subject understands that he

may take a dosage of the over-the-counter Regular Strength Tylenol® tablets right after the VAS rating has been recorded, if needed to manage foot pain.

14. Subject agrees and is able to complete the Subject Diary, as applicable.
15. 18 years of age or older.

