The pre-procedure washout phase comprises the 48-hour (2 day) period immediately preceding the pre-procedure evaluation phase, beginning upon waking on the first 24-hour period.

On each of the two consecutive days of the washout phase, the subject is required to record the specified measures on the washout phase subject record sheets provided by the test site in his or her home and to bring the completed forms to the test site on their pre-procedure evaluation visit.

The investigator will record the dates of the 48-hour washout phase on the subject's take-home record sheets based upon the timeframe required to satisfy the pre-procedure medication abstinence criteria, as applicable.

At the start of the pre-procedure washout phase, the subject commences his or her required abstinence from use of non-study related medications and therapies for the relief of foot pain and simultaneously commences the as-needed consumption of the study rescue medication – OTC Tylenol – for his or her foot pain, that will continue through to the end of the post-procedure evaluation phase.

PRE-PROCEDURE WASHOUT PHASE MEASURES

On each day of the two-day Pre-Procedure Washout Phase, the subject records the following measures on the supplied record sheets, as outlined in the STUDY TEST BATTERY section above.

- Visual Analog Scale (VAS) Foot Pain Rating
- Use of Study Rescue Medication (Tylenol)
- Use of Other Medications

DAY 1: PRE-PROCEDURE EVALUATIONS

The pre-procedure evaluation visit occurs on the day following successful completion of the two-day pre-procedure washout phase and comprises the following activities:

CONFIRMATION OF QUALIFYING VAS RATING

The investigator measures and records the 2 individual VAS foot pain ratings and calculates the average of the 2 VAS foot pain ratings recorded during the 48-hour pre-procedure washout phase. The 2-day average washout phase VAS foot pain rating must be 50 or greater for the subject to proceed with study participation. If the 2-day average washout phase VAS foot pain rating is less than 50, the subject's participation in the study ends at this time.

CONFIRMATION OF STUDY QUALIFICATION

If more than 7 days has passed since initial study qualification evaluation and the pre-procedure evaluation phase, the investigator will confirm with the subject that the information attained during study qualification evaluation has not since changed. If any

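### The VAS entry sets a 4-hour analgesic-free interval before a rating, but the rescue-medication text and inclusion criterion 13 require 6 hours after Tylenol; the 4 should become 6 (minor)

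*Combined protocol and SAP*

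**What the plan says.** Three current texts set a drug-free interval before a VAS rating.

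- **Study Test Battery, VAS Degree of Pain Rating:** "The subject is instructed to refrain from consuming any pain relief medication within 4 hours of recording a required VAS Degree of Pain Rating". The next sentence lets the subject take rescue medication straight after the rating.
- **Study Test Battery, Rescue Pain Medication Use:** "Subjects will be instructed not to record a VAS pain rating (whenever indicated) any sooner than six hours after they have consumed a dosage"; the drug meant is the rescue drug. The stated reason is that "a VAS rating is only to be recorded once the effect of any previously-consumed rescue pain medication has dissipated".
- **Inclusion Criteria, criterion 13:** the subject agrees to take no Tylenol "for at least 6 hours before a scheduled VAS foot pain rating is to be recorded".

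Rescue use starts before baseline. At the start of washout the subject "simultaneously commences the as-needed consumption of the study rescue medication". The two washout ratings must average at least 50 for the subject to proceed. The Day 1 rating and session 1 share a day: "The pre-procedure evaluation visit occurs on the day following successful completion of the two-day pre-procedure washout phase", and treatment starts within an hour of the pre-procedure measures. The endpoint VAS is taken within ten minutes of the end of session 12. Individual success is a fall of at least 30% from baseline to that rating.

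**The concern.** A rating taken five hours after Tylenol is acceptable under the VAS entry and forbidden by the other two texts. The VAS entry is where staff would look for how a rating is taken, because the Day 1 and post-procedure sections refer back to the test battery for method. The scale asks about pain at that moment, so a recent dose bears directly on the answer.

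Residual Tylenol could act in three places:

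- At washout, it could pull the two-day average below 50 and end a subject's participation.
- At baseline, it lowers the cutoff for a 30% fall, so it can hide a success.
- At the endpoint, it lowers the rating, so it can create a success.

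**Working it through.** **1. The three texts side by side**

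| Text | Interval | Drug named | Rating 5 h after Tylenol |
|---|---|---|---|
| VAS entry | 4 h | any pain relief medication | allowed |
| Rescue Pain Medication Use | 6 h | rescue drug | not allowed |
| Criterion 13 | 6 h | Tylenol | not allowed |

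No text says which interval governs.

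**2. Ratings covered.** Before the open-label period there are 2 (washout) + 1 (Day 1) + 11 (after sessions 1 to 11) + 1 (endpoint) + 3 (follow-up) = 18 scheduled ratings.

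**3. The plan's own figure.** The inputs, from Rationale for sample size, are 55% v 20%, two-sided alpha 0.05 and power 0.80. The pooled-variance formula is

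n = [1.96 × √(2 × 0.375 × 0.625) + 0.8416 × √(0.55 × 0.45 + 0.20 × 0.80)]² / 0.35² = (1.342 + 0.537)² / 0.1225 = 28.8, so 29 per group.

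This matches the plan (power 80.2%), and 29 / 0.917 = 31.6 gives 32. Correcting the interval changes none of these figures.

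**4. Direction for one subject (illustrative).** With a baseline of 70 mm, the success cutoff is 0.7 × 70 = 49 mm.

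- A 5 mm residual drug effect at the endpoint scores true endpoints of 49 to 54 mm as successes, which are true falls of 23% to 30%.
- The same 5 mm at baseline gives 65 mm and a cutoff of 0.7 × 65 = 45.5 mm, so true endpoints of 45.5 to 49 mm become failures.

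The two errors have opposite signs.

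**5. Possible scale (every input below is assumed).** Suppose 5% to 15% of subjects give the endpoint rating 4 to 6 hours after Tylenol, the residual effect d is 2 to 10 mm, and the endpoint minus cutoff is normal with SD 20 mm. The share of affected subjects misscored is Φ(z + d/20) − p, where p is the planned success rate and z its normal quantile.

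| d | Active (p = 0.55) | Placebo (p = 0.20) | Misscored of 64, at 5% and 15% affected |
|---|---|---|---|
| 2 mm | 3.9% | 2.9% | 0.11, 0.33 |
| 5 mm | 9.6% | 7.7% | 0.28, 0.83 |
| 10 mm | 18.4% | 16.6% | 0.56, 1.68 |

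For example, 0.15 × 32 × (0.184 + 0.166) = 1.68.

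By simulation at 32 per arm, the chance of observing the required 35-point gap is 0.472 with no affected ratings and 0.474 to 0.483 with equal use in both arms. At the extreme (15%, 10 mm) it is 0.571 if only active subjects are affected and 0.387 if only placebo subjects are.

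**6. Fisher's test near the 35-point boundary.** 0.35 × 32 = 11.2, so a gap of 12 subjects is needed. The p-values are 0.0040 for 18 v 6, 0.0097 for 18 v 7 and 0.0085 for 17 v 6. One misscored subject does not change significance in these examples.

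**The case against.** **The best defence of the text** is that the intervals are minimum waits. Six hours satisfies all three texts, every enrolled subject has agreed to six hours under criterion 13, and the rescue section covers every VAS and gives the reason. This stands, and it is why the point is minor. It does not clear the VAS entry, which still tells a reader that four hours is enough.

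**Four hours for other analgesics, six for Tylenol?** This reading fails. The VAS entry covers any pain relief medication, and its next sentence concerns the rescue drug.

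**Unseen material.** Appendix B (the VAS instructions for investigators) and the case report forms are not in the supplied text and may hold a last-dose check. That would reduce the practical risk but would not correct the protocol body.

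**Stronger readings that a reader might infer, and why the documents do not support them:**

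- *That per-protocol membership is undefined between 4 and 6 hours.* Statistical Methods limits that set to subjects who completed under the whole protocol. A dose at five hours breaches the six-hour rule, so the subject is out. Meeting the looser line does not bring the subject back in.
- *That the conflict makes an endpoint breach irreparable.* A breach found after session 12 cannot be undone under any single interval either.
- *That the primary result is materially at risk.* The dosing rate, residual effect and SD in the working have no source in the documents. The one-arm figures need use in one arm only, which nothing in the plan suggests. Dosing before baseline as well would offset much of the endpoint shift.

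**Conclusion.** The contradiction is certain: 4 hours in one place and 6 in two, all in current text. Its consequence is limited. It can let through ratings that the rescue section regards as possibly still drug-affected, at washout, baseline or endpoint. The size and direction cannot be computed from the documents. Under the assumed ranges, fewer than two of 64 subjects are misscored at the endpoint, and with equal use in the arms the chance of a 35-point gap barely moves. Membership of the primary ITT set, sample size and planned power do not depend on the interval. Severity is minor. It is still worth correcting, because the line governs the measure behind the primary endpoint and the correction is nearly free.

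**What to change.** **Core change.** In the VAS entry, replace 4 hours with at least 6 hours, so that it matches the rescue section and criterion 13 for every scheduled VAS, including washout and Day 1.

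**Left as a separate question.** Criteria 7 and 8 admit subjects on certain drugs if each "is willing and able to maintain that stable dosage throughout study participation", while criterion 11 and the rescue section bar other pain medication. Whether the pre-rating interval applies to those stable-dose drugs should be settled on its own. Until then, the word any in the VAS entry would carry the six hours to them too.

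**Low-cost support.**

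1. Ask the time of the last Tylenol dose before the Day 1 VAS and before session 12. The diary ("The subject will record each time a dose of the study rescue pain medication is taken as needed to manage foot pain") starts only with the first procedure, so it cannot serve for Day 1. The Day 1 question also does not reach the washout ratings made at home, where subjects need a reminder of the rule.
2. On Day 1, if the dose was less than 6 hours ago, delay the rating and session 1 together, later the same day. The longest wait is 6 hours.
3. Session 12 lasts 30 minutes, so the check is 6 h − 30 min = 5 h 30 min before its start. If the dose was more recent, start later that day or use the ±1 day window.
4. If a rating is still taken inside six hours, flag it and keep the observed value in the ITT analysis.

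**Cost.** One corrected line, one question at two visits, and an occasional delay of a few hours. Access to rescue medication, the responder definition, the sample size and ITT power are unchanged.

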| 
➤ VAS Degree of Pain Rating (Daily) |
| PRE-PROCEDURE EVALUATION PHASE |
| 
➤ Confirmation of Continued Study Qualification. 
PRE-PROCEDURE VARIABLES
 
➤ Baseline Foot Variables➤ Baseline Concomitant Medication and Therapy Use➤ Subject Demographics 
PRE-PROCEDURE MEASURES
 
➤ VAS Degree of Pain Rating➤ Neuropathic Pain Symptom Inventory (NPSI) |
| PROCEDURE ADMINISTRATION PHASE |
| 
PROCEDURE ADMINISTRATION PROTOCOL
 
Twelve 30-minute (15 minutes per foot) study procedure administrations with the Erchonia® FX-635™ over 6 consecutive weeks, 2 procedure administrations per week, administered at the test site.
 
PROCEDURE ADMINISTRATION PHASE MEASURES
 
➤ Subject Daily Diary➤ VAS Degree of Pain Rating➤ Adverse Events Evaluation |

POST-PROCEDURE ACTIVITIES

DAILY MEASURES: AT HOME

- Subject Daily Diary through to Week 4 Post-Procedure

STUDY ENDPOINT EVALUATION: AT TEST SITE

- VAS Degree of Pain Rating
- Neuropathic Pain Symptom Inventory (NPSI)
- Subject Satisfaction With Foot Pain Level
- Subject Perceived Group Allocation and Rationale
- Assessment Investigator Perceived Group Allocation and Rationale
- Adverse Events Evaluation

TWO WEEKS POST-PROCEDURE EVALUATION: AT HOME

- VAS Degree of Pain Rating
- Adverse Events Evaluation

FOUR WEEKS POST-PROCEDURE EVALUATION: AT HOME

- VAS Degree of Pain Rating
- Neuropathic Pain Symptom Inventory (NPSI)
- Subject Satisfaction With Foot Pain Level
- Adverse Events Evaluation

THREE MONTHS POST-PROCEDURE EVALUATION: AT HOME

- VAS Degree of Pain Rating
- Neuropathic Pain Symptom Inventory (NPSI)
- Subject Satisfaction With Foot Pain Level
- Adverse Events Evaluation

POST-STUDY OPEN-LABEL PLACEBO SUBJECT PROCEDURE ADMINISTRATION PERIOD

OPEN-LABEL PLACEBO SUBJECT PROCEDURE ADMINISTRATION PROTOCOL

Twelve 30-minute (15 minutes per foot) study procedure administrations with the Erchonia® FX-635™ over 6 consecutive weeks, 2 procedure administrations per week, administered at the test site.

OPEN-LABEL PROCEDURE ADMINISTRATION PHASE MEASURES

- Subject Daily Diary
- VAS Degree of Pain Rating
- Neuropathic Pain Symptom Inventory (NPSI)

- Subject Satisfaction With Foot Pain Level
- Adverse Events Evaluation

ADVERSE EVENTS

ADVERSE EVENTS DEFINITION

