6. K041139; 09/30/04: "The Erchonia EML Laser is indicated as an adjunct to liposuction procedures of the thighs, hips and stomach for reduction of pain associated with the recovery process."

Evaluation Time Point

The study end evaluation time point at which primary study success will be analyzed is at six weeks post-baseline, following completion of the 12th and final study procedure administration with the Erchonia® FX-635™.

Null Hypothesis: There will be no statistically significant difference in the proportion of individual successes, as defined, between the test and control groups.

Alternative Hypothesis: There will be a statistically significant difference in the proportion of individual successes, as defined, between the test and control groups, to the effect of 35% or greater.

SECONDARY EFFICACY OUTCOME MEASURES

Secondary efficacy outcome measures will be evaluated for the following four data sets:

1. The blinded data set only attained from subjects who were initially enrolled in either the test or placebo procedure group and will not include active procedure test data attained from placebo subjects who partook in the post-study open-label procedure administration period after blinding was broken.

For this group, the following secondary efficacy outcome measure will be evaluated:

- a) Change in VAS rating across and between all study evaluation time points within and between treatment groups
 - b) Change in scores on the Neuropathic Pain Symptom Inventory (NPSI) across and between all evaluation points within and between treatment groups
 - c) Differences in the use of rescue pain medication between procedure groups across study duration
2. The combined data set comprising the blinded data set attained from subjects who were initially enrolled in either the test or placebo procedure group, and the active procedure test data attained from placebo subjects who partook in the post-study open-label procedure administration period after blinding was broken, comparing combined test (blinded and non-blinded) to placebo data

For this group, the following secondary efficacy outcome measure will be evaluated:

- a) Change in VAS rating across and between all study evaluation time points to study endpoint evaluation within and between treatment groups
- b) Changes in scores on the Neuropathic Pain Symptom Inventory (NPSI) across and between all evaluation points to study endpoint evaluation within and between treatment groups

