For this group, the following secondary efficacy outcome measure will be evaluated:

- d) Change in VAS rating across and between all study evaluation time points to study endpoint evaluation within and between treatment groups

- e) Changes in scores on the Neuropathic Pain Symptom Inventory (NPSI) across and between all evaluation points to study endpoint evaluation within and between treatment groups
- f) Differences in the use of rescue pain medication between procedure groups across study duration to study endpoint evaluation.

STATISTICAL METHODS

Efficacy analysis will be according to the intent to treat (ITT) principle by last observation carried forward (LOCF).

Intent to Treat: Subjects will be included in the analysis if they were randomized to study procedure group, had a valid baseline visit including the required Low Back Pain VAS recordings; and received the first study procedure administration.

Last observation carried forward: Missing data will be handled by carrying forward the last observation.

Per-protocol analysis will also be performed for the set of all subjects who were randomized to procedure group and completed the study according to the full protocol.

STATISTICAL ANALYSIS

The primary analysis of efficacy will be through the application of:

- 1) **Fisher's exact test** to compare the proportion of success between the test and the control groups, considering that randomization has been diligently conducted and important covariates between the two groups are well balanced.
- 2) **Parametric ANCOVA model** analysis with the mean change from baseline to study endpoint in foot pain ratings on the VAS as the dependent variable, procedure group as the independent variable of interest and baseline average foot pain VAS rating as a covariate. A two-tailed significance level of 5% will be considered to be statistically significant.

Covariates: The following potential covariate baseline variables will be adjusted, as applicable, through application of an ANCOVA analysis for the continuous variables and linear regression analysis for categorical variables.

- ✓ Baseline VAS rating
- ✓ Baseline NPSI total score
- ✓ Duration of foot pain
- ✓ Time since Diabetes diagnosis
- ✓ Insulin dependent versus non-insulin dependent Diabetes
- ✓ Age
- ✓ Gender

Secondary Measures Analysis

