- The secondary measures that are continuous variables will be analyzed through parametric analysis using ANCOVA. A two-way significance level of 5% will be considered to be statistically significant.
- The secondary measures that are categorical will be evaluated through linear regression analysis.

Satisfaction with Study Outcome Ratings: will be tabulated according to category and reported as percentages. Satisfaction levels will be correlated with subject individual study success and recorded changes in foot pain VAS ratings from Baseline to post-procedure evaluations.

BLINDING EFFICACY EVALUATION

Statistical evaluation of blinding efficacy will be performed as follows:

- (i) The percentage of subjects who correctly perceived their procedure group allocation and the percentage of subjects who did not correctly perceive their procedure group allocation will be calculated.
- (ii) The percentage of times the assessment investigator correctly perceived subjects' procedure group allocation and the percentage of times the assessment investigator did not correctly perceive subjects' procedure group allocation will be calculated.
- (iii) The Fischer's Exact categorical analysis technique for comparison of proportion of successes (accurate procedure group allocation determination) between actual active and placebo subject groups will be performed.

It is anticipated that the results of the Fischer's Exact analysis will not be statistically significant; that is, it is anticipated that both subjects assigned to the active procedure group and subjects assigned to the placebo procedure group will demonstrate a high percentage of accuracy of group allocation determination if the study treatment proves efficacious. Similarly, it is anticipated that assessment investigators will demonstrate a high percentage of accuracy of group allocation determination for both subjects assigned to the active procedure group and subjects assigned to the placebo procedure group, if the study treatment proves efficacious. Therefore, it should be noted that lack of a statistically significant Fischer's Exact analysis result will be considered an indicator of study blinding efficacy, providing additional support to study outcome efficacy, particularly if appropriately supported by the reasoning statements, as explained below.

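### Washout Tylenol use is recorded before treatment, but no analysis uses it; it should be the baseline covariate for the rescue-use outcome

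*Combined protocol and SAP*

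**What the plan says.** The washout section (Days -2 and -1) starts the study analgesic before treatment: the subject stops other foot-pain remedies and "simultaneously commences the as-needed consumption of the study rescue medication". Its list of measures, to be recorded on each of the two days, has three items: the VAS foot pain rating, "Use of Study Rescue Medication (Tylenol") and use of other medications. The washout row of the Table of Subject Events carries only the first, "VAS Degree of Pain Rating (Daily").

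The Subject Daily Diary in the Study Test Battery covers a later window: "Commencing upon administration of the first Erchonia® FX-635™ laser procedure through to completion of the 4-week post-procedure evaluation phase". It therefore holds no pre-treatment value.

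Under Secondary Efficacy Outcome Measures, data set 1, the VAS outcome is "Change in VAS rating across and between all study evaluation time points within and between treatment groups", and the NPSI outcome is also worded as change. The rescue outcome is "Differences in the use of rescue pain medication between procedure groups across study duration". The other data sets repeat this pattern.

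On method, Secondary Measures Analysis says: "The secondary measures that are continuous variables will be analyzed through parametric analysis using ANCOVA". The covariate paragraph says: "The following potential covariate baseline variables will be adjusted, as applicable". It lists seven variables: baseline VAS, baseline NPSI total, duration of foot pain, time since diabetes diagnosis, insulin dependence, age and gender. Washout rescue use is not among them.

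**The concern.** Of the three secondary outcomes in the blinded data set, rescue use is the only one not tied to its own pre-treatment value, although that value is collected under the same as-needed rule that applies later. It is also the only planned pre-treatment record of how much study rescue medication a subject takes. The baseline medication history asks which pain remedies have been used, and requests dose and frequency only for medication taken for reasons other than pain.

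Rescue use matters beyond its own test. Tylenol is allowed throughout, so the comparison of its use helps a reader judge whether a difference in VAS came with more or less analgesic. A noisier comparison than necessary makes that judgement weaker. The phrase about adjusting as applicable also leaves the choice of covariate to be made after the data are seen.

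**Working it through.** **The plan's own figure.** The plan gives no sample size, SD or correlation for rescue use. Its only sample size is for the primary responder endpoint (55% against 20%, two-sided 5%, power 0.8). With a mean proportion of 0.375:

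n = [1.96·√(2 × 0.375 × 0.625) + 0.8416·√(0.55 × 0.45 + 0.20 × 0.80)]² / 0.35² = (1.342 + 0.537)² / 0.1225 = 28.8, so 29 per group.

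The plan's inflation gives 29/(1 − 0.083) = 31.62, so 32 per group. Both figures reproduce. The rest of the check uses 32 per arm.

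**Chance imbalance in washout use.** In SD units the group difference has standard error √(2/32) = 0.25. Its 95% range is ±1.96 × 0.25 = ±0.49 SD. The probability of an imbalance above 0.25 SD in either direction is 32%, and above 0.5 SD it is 4.6%.

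**Effect of adjustment.** Let r be the correlation between washout and on-study use. It is an assumption, shown over a range.

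- Variance of the adjusted group difference, relative to unadjusted: 1 − r².
- Extra subjects that an unadjusted analysis would need for the same precision: 1/(1 − r²) − 1.
- Detectable difference at 80% power, two-sided 5%: unadjusted (1.96 + 0.8416) × 0.25 = 0.70 SD; adjusted 0.70 × √(1 − r²).
- Part of a 0.5 SD washout imbalance that passes into the unadjusted comparison: 0.5 × r.
- Variance of a change score, taking equal SDs at washout and on study: 2(1 − r).

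| r (assumed) | Adjusted variance | Variance removed | Equivalent extra subjects | Detectable difference, adjusted | Carried over from 0.5 SD | Change-score variance |
|---|---|---|---|---|---|---|
| 0.3 | 0.91 | 9% | 10% | 0.67 SD | 0.15 SD | 1.40 |
| 0.5 | 0.75 | 25% | 33% | 0.61 SD | 0.25 SD | 1.00 |
| 0.7 | 0.51 | 49% | 96% | 0.50 SD | 0.35 SD | 0.60 |

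**Type I error.** In 40,000 simulated null trials with normal data and 32 per arm, the unadjusted test rejected 5.0% of the time at each of the three correlations. ANCOVA rejected 5.1%, 5.0% and 5.0%. Among only those trials whose washout imbalance exceeded 0.5 SD (about 4% to 5% of them), the unadjusted test rejected 11%, 19% and 34%, against about 5% to 6% with ANCOVA.

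**Change score.** At r = 0.3 a change score has 1.40 times the variance of the unadjusted value, and it gains nothing until r exceeds 0.5. ANCOVA has the lower variance in every row.

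**The case against.** The strongest reply is that allocation is randomised and stratified by site. A reader might infer that starting differences in Tylenol use will be read as a device effect. In the blinded data set the documents do not support that. Any starting difference there is chance, the unadjusted standard error already allows for it, and the overall error stays at 5%. The raised conditional rates above apply to fewer than one trial in twenty. This part of the reply stands.

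A reader might also infer that rescue use will be compared as a raw level. The plan does not say so. ANCOVA is planned for continuous secondary measures, baseline VAS and NPSI may be adjusted, and the study duration named in the outcome could be taken to include the washout. What can be said is that no baseline for rescue use is named. If the other covariates are used, r should be read as the correlation that remains after them, which may be smaller.

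A third tempting inference is that sites will fail to collect the washout record because the event table omits it. The table is offered as a summary, the washout section still requires the record, and subjects complete it at home on sheets supplied by the site. Loss of data is not shown.

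Finally, two days are a short baseline, taken just as subjects stop other remedies, and dose counts may include many zeros. The correlation may be low, and the variance formula is only approximate for such data. That limits the size of the gain, but it does not argue against naming the covariate.

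**Conclusion.** The point holds as a minor improvement to one secondary outcome. The plan collects a pre-treatment measure of rescue use, chooses ANCOVA, and does not connect the two. For the blinded data set there is no systematic bias and no loss of error control. The cost is a less precise comparison and less protection in a trial that happens to start unbalanced.

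The variance saved is 9%, 25% or 49% at r = 0.3, 0.5 or 0.7, with the lower figure the more plausible for a two-day baseline. These sizes rest on the assumed r, a roughly linear relation and 32 subjects per arm. The primary responder test and the sample size are unaffected.

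The statement about bias covers data set 1 only. The other data sets bring in open-label results from former placebo subjects, where randomisation does not protect the comparison; this covariate would not repair that.

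The mismatch between the washout section and the event table is real, but it is a consistency matter.

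**What to change.** 1. Define rescue use as a rate, such as doses per day, with the same unit in the washout and on study. State the on-study window, given that the diary ends four weeks after the last procedure.
2. In Secondary Measures Analysis, name washout rescue use (the rate over the two days) as the baseline covariate in the ANCOVA of the rescue-use outcome. Restrict it to that outcome: do not add it to the general covariate list, and do not replace the outcome with a change score.
3. Make the change before unblinding, so that the covariate is not chosen after the results are known.
4. In the washout row of the Table of Subject Events, add the rescue-medication and other-medication records so that it matches the washout section.

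The cost is a definition, one covariate (one degree of freedom) and one table row. The data are already required by the washout section.
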